### **3.6 | Statistical methods**

The data obtained throughout the study were evaluated by statistical analyzes (using IBM SPSS Statistics 23 software). Parametric tests were leveraged while evaluating research data based on the argument of Law of Large Numbers stating that (İnal & Günay, 2002) “The average of the results obtained from a large number of trials  $n \rightarrow \infty$  will tend to become closer to the expected value”. The evaluation of the research data provides frequency distribution (number, percentage) for categorical variables and descriptive statistics (mean, standard deviation) for numerical variables. Difference between categorical variables with two groups was tested using Independent t-Test whereas the difference between the categorical variables with more than two groups was tested with "One Way Variance Analysis" (ANOVA). Following the analysis; initially, the homogeneity of the variance was controlled by Levene Test and then the group or groups causing the difference were controlled by "Multiple Comparison Test". The difference between the groups regarding the variables that provide variance homogeneity was evaluated via Bonferonni while Tamhane's T2 test was used to examine the difference between groups in variables that do not comply with variance homogeneity. In addition, the difference between the two numerical variables over time was evaluated with Dependent Sample t Test while the relationship between the two categorical variables was examined with the Chi-Square test. Statistical significance was considered as  $p < 0.05$ .

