### **Aim of the study and hypotheses**

The purpose of this study is to evaluate the effectiveness of the Nurse Led Transitional Care Model. The hypotheses are as follows;

H0: Nursing care carried out in collaboration with a multidisciplinary team in line with TCM for elderly patients who have undergone open heart surgery has no effect on decreasing the patients' functional autonomy, their quality of life levels and the rate of repeated post discharge referrals to hospital and rehospitalization.

H1: Nursing care carried out in collaboration with a multidisciplinary team in line with TCM for elderly patients who have undergone open heart surgery may improve the patients' functional autonomy, their quality of life levels and decrease the rate of repeated post discharge referrals to hospital and rehospitalization.

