## **STUDY PROTOCOL**

### **1 | Study design**

The research was carried out between November 2017 and December 2018 in a pretest-posttest design structured in accordance with the CONSORT guidelines (Figure 1), as a randomized controlled intervention study with parallel groups (Schulz, Altman, & Moher, 2010).

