### **3.2 | Allocation**

Patients were randomly assigned to the intervention and control groups respectively in line with the inclusion criteria of sampling through a computerized randomization system. Patients reached in the pre-application period (n = 6) were also included in the sample of the study, considering possible patient loss throughout the study. Ultimately, 66 patients were included in this study; the subjects were individually numbered and randomized by an individual outside of the investigation team using the website software program Research Randomizer

(<http://www.random.org>) to divide the subjects into the intervention group (33 patients) and control group (33 patients). The patients were not blinded. If someone declined, the next patient from the list was invited instead.

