### **3.5 | Intervention**

Patients in intervention group were given care based on the 'Nurse Led Transitional Care Model Protocol' (Figure 2) until the post discharge 9th week starting from date of hospitalization. Patients in control group were given standard care services.

The patients in both groups were interviewed face-to-face by the Researcher (Coordinator Nurse) in the first twenty-four hours following their admission to the hospital and administered "Introductory Information Form", "The Functional Autonomy Measurement System" and "SF-36 Quality of Life Scale". In addition, the Researcher (Coordinator Nurse) reached the patients in both groups after nine weeks following their discharge and reapplied the "The Functional Autonomy Measurement System" and "SF-36 Quality of Life Scale". Six months following their discharge these patients were called by phone and checked up on their repeated referrals to hospital and/or rehospitalization.

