### **4 | Study Limitations And Recommendations For Future Research**

[figure not shown]
This study has some limitatons. Firstly, the sample size is quite small and the research was carried out in a single center with patients who lived within a 50 km. distance from the hospital where the study was carried out due to transportation limitations. No conclusions have been derived for patients residing at a greater distance. Secondly, WHO currently defines the elderly as individuals 65 years old and above. However, based on the cultural values of our country, average life expectancy and mean retirement age foreseen in our society, the population of elderly patients included in our study consisted of patients at 60 years of age and older.

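### No baseline-adjusted comparison of the arms is specified for functional autonomy and SF-36, and the score used in the t-test is not stated

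*Combined protocol and SAP*

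**What the plan says.** Section 1 describes a randomised parallel-group study "in a pretest-posttest design structured in accordance with the CONSORT guidelines". Under section 3.5, the functional autonomy scale and SF-36 are administered to both arms within a day of admission. The researcher then "reached the patients in both groups after nine weeks following their discharge and reapplied" the same two instruments; the week-9 visit in Figure 2 lists them too.

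The alternative hypothesis is that the care model may improve patients' "functional autonomy, their quality of life levels and decrease the rate of repeated post discharge referrals to hospital and rehospitalization". That is a statement about one arm against the other.

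Section 3.6 gives the full list of methods: descriptive statistics, independent t-test, one-way ANOVA with post hoc comparisons, paired t-test and chi-square. Two sentences could apply to the scales:

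- "Difference between categorical variables with two groups was tested using Independent t-Test". No outcome, time point or score is named.
- "the difference between the two numerical variables over time was evaluated with Dependent Sample t Test". No arm is mentioned.

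ANCOVA, regression, a repeated-measures model or any other baseline adjustment appears nowhere in the document.

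**The concern.** A pretest-posttest trial collects a baseline value of each scale from every patient, yet no listed method uses it to sharpen the comparison of the arms. Three consequences follow.

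- **The between-arm test cannot be identified.** The independent t-test is presumably the one meant for these scales, but it could be run on week-9 scores or on change from admission. The two have different power, and a choice left open can be made after the results are seen.
- **Precision is given up.** Section 4 itself concedes that "the sample size is quite small".
- **The paired test answers another question.** It compares patients with themselves, so recovery after surgery in both arms would make it significant in both. Nothing in the plan says efficacy will be concluded from these tests, but nothing limits them to description.

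**Working it through.** **Inputs from the document.** 33 patients per arm were randomised (section 3.2). The planned number was 30 per arm (section 3.3). Six patients were added "considering possible patient loss throughout the study", so losing six evenly would leave 30 per arm. The significance level is 0.05 (section 3.6); sidedness is not stated and is taken as two-sided.

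**Assumptions, none of them in the document.** True effect d = 0.6 SD; pre-post correlation r from 0 to 0.7; equal SDs at the two visits.

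The plan gives no power figure for these scales to reproduce. Its 30 per group cannot be derived either, because no difference to detect is stated. That is a separate matter, and the figure is used here only as a number of patients.

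**Step 1: error variance relative to a week-9 t-test (= 1).**

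- Change score: 2(1 − r)
- ANCOVA: 1 − r²
- Ratio of ANCOVA to change score: (1 − r²) / [2(1 − r)] = (1 + r)/2, which is below 1 for every r below 1

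**Step 2: power.** Noncentral t with noncentrality d* × √(n/2). For the week-9 test d* = d; for change d* = d/√(2(1 − r)); both have 2n − 2 df. For ANCOVA d* = d/√(1 − r²) with 2n − 3 df. At n = 33 the week-9 noncentrality is 0.6 × √16.5 = 2.437, giving 67.0% power at any r.

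At r = 0.5, d* for change is 0.6/√1 = 0.600, so power is again 67.0%. For ANCOVA d* is 0.6/√0.75 = 0.693, giving 79.1%.

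| r | Week-9 t, n = 33 | Change t, n = 33 | ANCOVA, n = 33 | Week-9 t, n = 30 | ANCOVA, n = 30 |
|---|---|---|---|---|---|
| 0.2 | 67.0% | 47.5% | 68.8% | 62.8% | 64.5% |
| 0.3 | 67.0% | 52.8% | 71.1% | 62.8% | 66.8% |
| 0.5 | 67.0% | 67.0% | 79.1% | 62.8% | 75.1% |
| 0.7 | 67.0% | 87.3% | 91.9% | 62.8% | 89.2% |

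Simulation with 40,000 trials per setting agrees within one point. Type I error is 0.048 to 0.052 for all three analyses.

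**Step 3: small-sample cost of the covariate.** Estimating the slope multiplies the ANCOVA variance by about 1 + 1/(2n − 4), which is 1 + 1/62 = 1.016 at n = 33. ANCOVA power then becomes 66.3% at r = 0, 66.7% at 0.1, 68.1% at 0.2, 70.4% at 0.3, 78.5% at 0.5 and 91.5% at 0.7. The ordering in the table does not change. At r of about 0.1 or less, ANCOVA is under one point below the week-9 test.

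**Step 4: what the gain is worth in patients.** Ignoring that small cost, 33/(1 − r²) per arm is 36.3 at r = 0.3, 44.0 at 0.5 and 64.7 at 0.7.

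**Step 5: paired tests read arm by arm.** Suppose both arms truly change by the same amount, expressed in SDs of the change score. If p is the power of a paired t-test at n = 33, exactly one arm is significant with probability 2p(1 − p). Only the intervention arm is significant with half that probability.

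| Change (SD of change) | p | Exactly one arm | Intervention arm only |
|---|---|---|---|
| 0 | 0.050 | 9.5% | 4.8% |
| 0.2 | 0.200 | 32.0% | 16.0% |
| 0.35 | 0.496 | 50.0% | 25.0% |
| 0.5 | 0.795 | 32.6% | 16.3% |
| 0.65 | 0.952 | 9.2% | 4.6% |
| 0.8 | 0.994 | 1.3% | 0.6% |

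**The case against.** The strongest reply is that a t-test between randomised arms is valid, so this is advice on efficiency, and its size rests on a correlation the document does not give. Baseline is taken before open heart surgery and follow-up nine weeks after discharge, so a high r cannot be presumed. At r of 0.2 to 0.3 the gain over a week-9 t-test is only about 1 to 4 points. That stands, and is why a range is shown. It does not remove the unstated score: at those same correlations a change-score t-test would be about 14 to 20 points below the week-9 test.

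Four further points stand as qualifications.

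- Section 3.6 does not tie the independent t-test to these scales. That link is an inference.
- The statement that there is no bias presumes sound randomisation and complete week-9 data. The document leaves questions on both: section 2.1 excludes patients who die or suffer a relevant illness during the study, and sections 3.1 and 3.2 describe assignment differently. ANCOVA repairs neither.
- The rates in step 5 are in SDs of the change score, while the 0.6 SD effect is in SDs of the outcome; the two units coincide only at r = 0.5. The misleading pattern, intervention arm alone significant, has at most half the probability of exactly one significant arm, and no passage says it will be read as efficacy.
- The study is reported in the past tense, so a new analysis may have to be post hoc.

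**Conclusion.** The concern holds. The plan specifies no baseline-adjusted comparison of the arms for functional autonomy or SF-36, and does not say which score the independent t-test uses. Adjusting for a baseline already collected is the better method, at almost no cost.

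Under the stated assumptions, ANCOVA adds about 2, 4, 12 and 25 points of power to a week-9 t-test at r = 0.2, 0.3, 0.5 and 0.7. Over a change-score t-test it adds about 21, 18, 12 and 5. Allowing for slope estimation takes less than one point off each gain. At r near zero there is nothing to gain.

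This is a weakness of precision and specification that should be fixed. It does not by itself invalidate the trial's comparison of the arms.

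**What to change.** In section 3.6, for functional autonomy and each SF-36 score:

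1. State that the treatment effect is estimated by ANCOVA: week-9 score on arm plus the baseline value of the same scale. Report the adjusted between-arm difference with its 95% confidence interval.
2. If an independent t-test is also reported, say whether it uses the week-9 or the change score.
3. Label the paired t-tests as descriptive, with no conclusion about efficacy drawn from them.

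The change does not apply to hospital referrals or rehospitalisation, which have no pretest. It does not settle the primary outcome, multiplicity across the SF-36 scores or missing week-9 data; each needs its own statement.

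The cost is wording in section 3.6 and one model per score in the SPSS package already in use, with no new patients or measurements. Because the study ran from November 2017 to December 2018, an ANCOVA adopted after the data were seen must be disclosed as post hoc.

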#### **2.1 | Inclusion and exclusion criteria**

Inclusion criteria for participation in the study are as follows: The Patient should a) be hospitalized for the first time and for elective open heart surgery; b) have no other surgical intervention other than an open heart surgery, c) have no psychological and mental disorders, d) have no major chronic problems such as kidney problems, neurological problems or cancer, e) be able to speak Turkish, f) be available to be communicated by phone, g) provide consent to participate in the study, h) live at a maximum distance of 50 km from the hospital (for easy access during post-discharge follow-up visits). Exclusion criteria are as follows: The Patient should a) ask to leave the study, b) be exposed to a disease or trauma that may affect his/her functional autonomy during the study, c) die throughout the study.

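### The planned paired t-test of change spans open heart surgery and recovery in both arms, so it cannot test H1, and section 3.6 does not say that a between-arm comparison decides

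*Combined protocol and SAP*

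**What the plan says.** Section 1 describes a randomised parallel-group trial, "in a pretest-posttest design structured in accordance with the CONSORT guidelines". Section 3.5 gives the two scales to both arms at the same two times. The first is "in the first twenty-four hours following their admission to the hospital"; for the second, the researcher "reached the patients in both groups after nine weeks following their discharge". Under section 2.1 every patient must "be hospitalized for the first time and for elective open heart surgery".

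Section 3.6 gives one method for change over time: "the difference between the two numerical variables over time was evaluated with Dependent Sample t Test". The same sentence goes on to assign the chi-square test to pairs of categorical variables. Earlier in the section stands: "Difference between categorical variables with two groups was tested using Independent t-Test". One threshold, 0.05, serves every test.

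Section 3.6 does not say which outcome the independent t-test is applied to. It specifies no baseline-adjusted model or group-by-time test, and names no test as the one that decides H1.

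**The concern.** H1 is a claim about the effect of TCM, and in a randomised trial only a contrast between the arms can answer it. The one method that section 3.6 ties to the pretest-posttest structure is a paired test, which cannot compare two independent groups. Applied within an arm, it tests surgery plus recovery, plus TCM in the intervention arm. Applied to all patients together, it says nothing about TCM.

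What is at stake is how the result is read. A report that scores improved significantly with TCM but not with standard care would be compatible with section 3.6 as written. Yet the difference between a significant and a non-significant p-value is not a test of the difference between arms, and reading it as one gives up what randomisation provides. This holds even when the paired t-test's own assumptions are met.

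**Working it through.** **Timing.** Admission is for elective surgery (section 2.1), and the pretest falls within a day of admission (section 3.5). The posttest is nine weeks after discharge in both arms (section 3.5). So, in expectation:

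- control arm change = surgery and recovery under standard care;
- TCM arm change = surgery and recovery + TCM effect.

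The paired test in the TCM arm tests whether that sum is zero. Only the difference between the two lines isolates TCM.

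**Inputs for the size.**

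- 33 patients per arm (section 3.2); 30 per arm (section 3.3) as a check.
- Level 0.05 (section 3.6). Sidedness is not stated; two-sided is assumed.
- Standardised change dz = mean change / SD of change. The documents give neither quantity, so dz is an assumption and is varied.
- No TCM effect, so dz is the same in both arms.

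The plan states no figure of its own for this point. The result does not depend on the sample-size derivation in section 3.3.

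**Formulas.** Let p(dz) be the power of a two-sided paired t-test, from the noncentral t distribution with n − 1 degrees of freedom and noncentrality dz × √n. The arms are independent, so:

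- P(significant in TCM, not in control) = p(1 − p);
- P(both significant) = p².

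The first expression has its maximum, 0.25, at p = 0.5.

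**Results, one endpoint, no TCM effect** (products use unrounded p):

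| dz | p, n = 33 | TCM only, n = 33 | TCM only, n = 30 |
|---|---|---|---|
| 0 | 0.050 | 4.8% | 4.8% |
| 0.2 | 0.200 | 16.0% | 15.1% |
| 0.3 | 0.387 | 23.7% | 22.9% |
| 0.35 | 0.496 | 25.0% | 24.8% |
| 0.5 | 0.795 | 16.3% | 18.6% |
| 0.6 | 0.916 | 7.7% | 10.0% |
| 0.8 | 0.994 | 0.6% | 1.1% |
| 1.0 | 1.000 | 0.02% | 0.04% |

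For example, at dz = 0.35 and n = 33: 0.496 × 0.504 = 0.250. At dz = 0.8, both arms are significant in 0.994² ≈ 99% of trials.

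**Simulation check.** In 100,000 simulated trials with 33 per arm, the TCM-only pattern occurred in 4.8%, 16.1%, 25.1%, 16.5% and 0.7% at dz 0, 0.2, 0.35, 0.5 and 0.8. In the same trials an independent t-test on change scores was significant in 4.9% to 5.0% throughout. Half of 5% falls in each direction, so it falsely favours TCM in about 2.5%.

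**The case against.** The strongest reply is that this describes a possible misuse and not a stated plan. Section 3.6 nowhere says that H1 will be judged by setting one arm's p-value against the other's. The paired-test clause does not mention arms at all, and the section lists an independent t-test, which is a valid between-arm test if applied to week-9 or change scores. A paired test reported beside such a comparison is not in itself an error.

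That largely stands, and it rules out two readings a reader might infer. One is that the plan decides H1 on within-arm significance; the text neither requires nor excludes this. The other is that the plan has no between-arm test; it has one, with its outcome and its role left open. The neighbouring analysis of variance for more than two groups cannot refer to the trial's two arms. So that part of section 3.6 must at least partly concern other groupings, and the independent t-test cannot be assumed to mean TCM against control on the two scales.

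A second reply is that 25% is a worst case. That is right: it is the ceiling of p(1 − p), reached only near dz 0.35, and with strong recovery the pattern almost disappears. But in that case a significant change in the TCM arm is nearly certain whether or not TCM works, so it still carries no information about H1.

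A third is that the calculation treats the common change as improvement. If scores fall instead, the mirror pattern (significant decline in control, not in TCM) would favour TCM and has the same probability.

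Finally, dropping within-arm p-values altogether is partly a matter of taste. What is needed is that they do not serve as evidence for TCM.

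**Conclusion.** The point holds as a conditional one. The paired test cannot answer H1, because surgery and recovery lie between its two measurements in every patient, and section 3.6 does not name the between-arm analysis that would. If H1 were supported by significance in TCM alone, the false-support rate for one endpoint with 33 per arm would range from under 1% to 25%, depending on a common change that the documents do not give. The comparison figure is 2.5% for a two-sided between-arm test.

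The 25% should not be read as the expected error rate of this trial. It rests on an assumed dz near 0.35, two-sided testing, full follow-up of 33 per arm and that particular misuse. What does not depend on dz is that the within-arm test addresses the wrong contrast. The change should be made; it is a correction of method and does not show that the trial's conclusion is wrong.

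**What to change.** Edit only the paired-test clause in section 3.6. Keep the chi-square clause in the same sentence: it is the only listed test for two categorical variables, and so the natural one for hospital referral and rehospitalisation by arm, which are also part of H1. Replacement text:

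> Change from admission to week 9 is described in each arm as mean change with 95% CI. Support for H1 on functional autonomy and SF-36 is judged only on the between-arm difference at week 9, adjusted for the admission score (ANCOVA), or on the Independent t-Test of change scores, reported with its 95% CI; within-arm tests are not used as evidence for TCM.

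One of the two between-arm analyses should be named as deciding. If outcome data have already been seen, the report should say when that choice was made.

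The cost is a small text edit. Both arms already have both measurements, so no new data are needed. The downside is fewer significant p-values to report.

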### **4 | Study Limitations And Recommendations For Future Research**

[figure not shown]
This study has some limitatons. Firstly, the sample size is quite small and the research was carried out in a single center with patients who lived within a 50 km. distance from the hospital where the study was carried out due to transportation limitations. No conclusions have been derived for patients residing at a greater distance. Secondly, WHO currently defines the elderly as individuals 65 years old and above. However, based on the cultural values of our country, average life expectancy and mean retirement age foreseen in our society, the population of elderly patients included in our study consisted of patients at 60 years of age and older.

### **5 | Acknowledgements**

Authors declared no financial support while investigating and writing this paper.

### **6 | Results point of contact**

Abant İzzet Baysal University, Abant İzzet Baysal University Clinical Research Ethics Committee, [contact] [name] , Email: [contact]

**Figure 1.** CONSORT diagram of the trial flow

| Patients at 60 years of age and older who are decided to have open heart surgery   |   |  |   |
|---|---|--|---|
| 
Coordinator Nurse:
 
 
✓ Taking the Patient's Medical History
 
✓ Hospital and Clinic Promotion
 
✓ Providing Training Guide
 
✓ Daily Regular Patient Visits
 
✓ Coordinating the Healthcare Services
 
   |   |  |   |
| 
Case analysis (pre-operative period)
 
Team members: physician, nurse, coordinator nurse, physiotherapist, dietician, evaluation of caregiving family member
   |   |  |   |
| 
Coordinator Nurse:
Post-operation training for patients
Daily Patient Visits
  | 
Clinic Nurses:
To execute healthcare services in line with designated healthcare plan
Completion of the practices in the Clinical Pathway (post-op 1st, 2nd, 3rd, 4th, 5... days)
 | 
Dietician:
To plan a nutrition program for the patient and train the patient accordingly
 | 
Physiotherapist:
To plan the physical activity and exercise program for the patient and train the patient accordingly
 |
| 
Case analysis (post-operative period)
 
Team members: physician, nurse, coordinator nurse, physiotherapist, dietician, evaluation of caregiving family member
  |   |  |   |
| 
Coordinator Nurse:
Post-operation training for patients
Daily Patient Visits
  | 
Clinic Nurses:
To execute healthcare services in line with designated healthcare plan
Completion of the practices in the Clinical Pathway (post-op 1st, 2nd, 3rd, 4th, 5... days)
 | 
Dietician:
To plan a nutrition program for the patient and train the patient accordingly
 | 
Physiotherapist:
To plan the physical activity and exercise program for the patient and train the patient accordingly
 |
| 
Coordinator Nurse:
 
 
✓ Home visit within 24 hours after hospital discharge; 
 
• The patient's living conditions,
 
• Understanding and executing the proposed treatment and drug regimen,
 
• Assessment of the performance on executing practices to accelerate the recovery of the patient
 
• To continue planning and executing healthcare services
 
 
 
✓ Providing consultancy service via telephone to the patient and family members within post discharge first week
 
   |   |  |   |
| 
Coordinator Nurse:
 
 
✓ Home visits at post discharge 2nd and 6th weeks; 
 
• "Post-Discharge Home Follow-Up Form of Elderly Person Undergoing Open Heart Surgery"
 
• "Post-Discharge Recurrent Hospital Admission Follow-Up Form"
 
• Providing training and consultancy in cooperation with the team members for the detected problems
 
• Follow-Up for the detected problems
 
 
 
   |   |  |   |
| 
Coordinator Nurse:
 
 
✓ Home visits at post discharge 9th week; 
 
• "Post-Discharge Home Follow-Up Form of Elderly Person Undergoing Open Heart Surgery"
 
• "Post-Discharge Recurrent Hospital Admission Follow-Up Form"
 
• Providing training and consultancy in cooperation with the team members for the detected problems
 
• Follow-Up for the detected problems
 
• 'The Functional Autonomy Measurement System',
 
• 'SF-36 Quality of Life Scale'
 
 
 
 |   |  |   |
| 
Coordinator Nurse:
 
 
✓ Telephone Communication at post discharge 6th month 
 
• "Post-Discharge Recurrent Hospital Admission Follow-Up Form"
 
 
 
   |   |  |   |

**Figure 2.**'Nurse Led Transitional Care Model Protocol'
